3.2.3. Missing Data and Outliers

Every effort will be made to obtain required data at each scheduled evaluation from all participants who have been enrolled. In situations where it is not possible to obtain all data, it may be necessary to impute missing data. These situations are described below. Unless otherwise specified, all other missing data will not be imputed.

3.2.3.1. Missing Severity or Relationship for Adverse Events

AEs with missing severity will have the severity imputed as "Grade 3" for the AE tabulations. AEs with missing relationship to study drug will have the relationship imputed as 'Definite' for the AE tabulations if the AE started after initiation of study drugs.

3.2.3.2. Imputation of Incomplete Dates

An incomplete date occurs when the exact date an event occurred or ended cannot be obtained from a participant. The database contains data fields for month, day, and year. A date is incomplete if at least one of these three fields is not known. For many of the planned analyses, a complete date is necessary to determine if the event should be included in the analysis (ie, if the event is treatment-emergent) or to establish the duration of an event. In such cases, incomplete dates will be imputed.

For the purposes of handling partially reported start and stop dates for an event the following algorithm will be applied:

1) For onset date:

- a) If only the day part of the onset date is missing and occurs in the same month and year as the date of dose of study drug, the date of dose of study drug will be used as the onset date. Otherwise, the first day of the month will be used to complete the onset date.
- b) If the day and month parts of the onset date are missing and occur in the same year as the dose of study drug, the date of the dose of study drug will be used as the onset date.

 Otherwise, January 1st will be used to complete the onset date.
- c) If the onset date is completely missing, the date of the dose of study drug will be used as the onset date.

2) For end date:

- a) If only the day part of the end date is missing, the last day of the month will be used to complete the end date.
- b) If the day and month parts of the end date are missing, December 31st will be used to complete the end date.
- c) If the end date is completely missing, the maximum of the participant's study discontinuation date or date of last contact will be used as the end date.

If any imputed start date causes the start date to occur after the end date, the end date will be used for the imputation of the start date. If any imputed end date causes the end date to occur prior to the start date of the event, the start date of the event will be used for the imputation of the end date.

3.2.4. Presentations by Study Visit

When data are collected serially over time, individual data presentations may include by-study visit displays. By-study visit displays will only be summarized up to 30 days after last treatment. Visits will be presented according to the nominal visit as obtained from the eCRF. If multiple observations are collected at a scheduled visit, the closest observation to the target day will be chosen. If two observations have equal distance from the target day but one is earlier and the other is later than the target day, the earlier observation will be chosen. Unscheduled assessments will be included in the listings.

3.2.5. Presentations by Worst Case

When data are collected serially over time, individual data presentations may include "worst case on study" displays. In those situations, both scheduled and unscheduled assessments up to 30 days after last treatment will be included.

3.2.6. Definitions and Terminology

Age

Age is age at informed consent and is as captured on the eCRF.

CONFIDENTIAL Page 19 19 November 2024

Baseline Value

For purposes of analysis, the baseline value is defined as the last non-missing value obtained prior to initiation of study drug.

Cycle 1, Day 1 (Baseline)

Cycle 1, Day 1 is the earliest day that study drug is initiated.

Study Day

Study Day is defined relative to Baseline (Cycle 1, Day 1). Thus, the study day of an event is calculated as:

Study Day = event date – date of Cycle 1, Day 1 (+ 1, if event date \geq date of Cycle 1, Day 1).

Study Visit

Study Visit is the nominal visit as recorded on the eCRF.

Change from Baseline

Change from baseline for a given endpoint is defined as the Study Day X value minus the Baseline Value.

Days on Study

Days on study is the number of days from Cycle 1, Day 1 to the date of study completion as recorded on the End of Study eCRF page.

Adverse Event (AE)

An AE is any untoward medical occurrence in a patient or clinical study participant, temporally associated with the use of study drug(s), whether or not considered related to the study drug(s). An AE can therefore be any unfavorable and unintended sign (including an abnormal laboratory finding), symptom, or disease (new or exacerbated) temporally associated with the use of study drug(s).

Treatment-emergent Adverse Event (TEAE)

A TEAE is an AE that occurred during the study on or after the initiation of study drug through 30 days after last dose of study drugs. Additionally, it is assumed that an AE which was reported to have started on Cycle 1, Day 1 without an associated onset time occurred on or after initiation of study drug. Treatment-emergent serious adverse events (TESAEs) are collected through 90 days post last dose of study drug.

Adverse Event of Special Interest (AESI)

Any AE (serious or non-serious) of scientific and medical concern for which ongoing monitoring and communication by the investigator to the Sponsor or designee may be appropriate. Such events may require further investigation to characterize and understand them.

Because lerapolturev is an immunotherapeutic administered by intratumoral injection, AESIs fall into 2 categories: (1) AEs related to lerapolturev administration (ie, injection site reaction [ISR]), and (2) AEs related to cytokine release syndrome [CRS] and immune effector cell-associated neurotoxicity syndrome [ICANS], which can occur when the body's immune cells release a bolus of inflammatory cytokines in response to an immunotherapy.

AESIs are collected through 90 days post last dose of study drug.

Immune-Related Adverse Events (irAEs)

Any adverse event affecting an organ system through an autoimmune or inflammatory mechanism, whereby the immune system is acting against normal tissue. The list of terms to identify irAEs is as

follows: (1) high level term (HLT): Colitis (excl infective); (2) HLT: Lower respiratory tract inflammatory and immunologic conditions; (3) HLT: Hepatocellular damage and hepatitis NEC; (4) HLT: Hypothalamic and pituitary disorders NEC; (5) HLT: Adrenal cortical hypofunctions; (6) HLT: Diabetes mellitus (incl subtypes); (7) HLT: Nephritis NEC; (8) HLT: Encephalitis NEC; (9) Preferred term (PT): Toxic epidermal necrolysis; (10) PT: Severe cutaneous adverse reaction; (11) PT: SJS-TEN overlap; (12) PT: Stevens-Johnson syndrome. Recommendations for study drug management in the event of an irAE are described in Protocol Section 5.5.

irAEs are collected through 90 days post last dose of study drug.

Concomitant Medications

Concomitant medications are those medications taken on or after the initiation of study drugs through 30 days post last dose of study drug. This definition includes medications started prior to initiation of study drugs and continuing concomitantly with study drugs.

Prior Medications

Prior medications are those medications taken and discontinued prior to initiation of study drugs.

Complete Response (CR)

A CR is defined by:

- disappearance of all target lesions AND
- disappearance of all non-target lesions AND
- all lymph nodes must be non-pathological in size (< 10 mm short axis) AND
- no appearance of new unequivocal lesions.

Partial Response (PR)

A PR is defined by:

- \geq 30% decrease in the sum of diameters of target lesions, taking as reference the baseline sum diameters AND
- non-CR / non-PD or not evaluated non-target lesions AND
- no appearance of new unequivocal lesions.

Stable Disease (SD)

Stable disease (SD) is defined by:

- non-PR / non-PD of target lesions AND
- non-PD or not all evaluated of non-target lesions AND
- no appearance of new unequivocal lesions.

Progressive Disease (PD)

Progressive disease (PD) is defined by:

- \geq 20% increase in the sum of diameters of target lesions, taking as reference the smallest sum on study (this includes the baseline sum if that is the smallest on study) and an absolute increase of at least 5 mm OR
- unequivocal progression of non-target lesions OR
- appearance of one or more new lesions.

Duration of Response (DOR)

DOR is defined as time since a confirmed objective response (CR or PR) is first observed (ie, the scan date when the response originally occurred prior to confirmation) until unequivocal disease

progression (PD) or death, whichever occurs first. Participants will be censored at the date of the last imaging, if there is no date for PD or death.

Objective Response Rate (ORR)

ORR is defined as the proportion of participants achieving confirmed CR or confirmed PR.

Durable Response Rate (DRR)

DRR is defined as the proportion of participants with confirmed CR or confirmed PR lasting ≥ 6 months.

Overall Survival (OS)

OS is defined as time from start of treatment until death from any cause or last follow-up if participant is alive. Participants who are lost to follow-up will be censored at the last date of contact. The primary analysis will include the following subgroups:

- Participants who received lerapolturev monotherapy
- Participants who received lerapolturev + anti-PD-1
- Participants who crossed over from lerapolturev monotherapy to lerapolturev + anti-PD-1 from treatment group assignment until death from any cause or last follow-up, if participant is alive
- Participants who crossed over from lerapolturev monotherapy to lerapolturev + anti-PD-1 from time of crossover until death from any cause or last follow-up if participant is alive

Progression Free Survival (PFS)

PFS is defined as time (number of months) from start of treatment until date of documented radiologic disease progression or death due to any cause, whichever comes first. Participants not meeting this definition will be censored at the date of the last imaging. The primary analysis will include the following subgroups:

- Participants who received lerapolturev monotherapy
- Participants who received lerapolturev + anti-PD-1
- Participants who crossed over from lerapolturev monotherapy to lerapolturev + anti-PD-1 from treatment group assignment until death from any cause or last imaging, if participant is alive
- Participants who crossed over from lerapolturev monotherapy to lerapolturev + anti-PD-1 from time of crossover until death from any cause or last imaging if participant is alive

Disease Control Rate (DCR)

DCR is defined as the proportion of participants achieving confirmed CR, confirmed PR, or SD as best response.

Disease Control Rate-6 Months (DCR-6mo)

DCR is defined as the proportion of participants achieving confirmed CR for any duration, confirmed PR for any duration, or SD for ≥ 6 months as best response.

Treatment Period

Treatment period is defined as Cycle 1, Day 1 of study to the EOT.

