2 OBJECTIVES AND ENDPOINTS

2.1 Objectives and Endpoints

Objectives	Endpoints/Evaluation Criteria			
Primary				
To evaluate the anti- tumor activity of lerapolturev with and without anti-PD-1, in participants who have failed anti-PD-1/L1- based therapy	Overall Response Rate (ORR): the proportion of participants achieving confirmed complete (CR) or partial response (PR), per RECIST 1.1 criteria.			
To evaluate the safety/tolerability of lerapolturev with and without anti-PD-1, in participants who have failed anti-PD-1/L1-based therapy To evaluate the effect of	 The frequency and severity of treatment-emergent adverse events (AE) via Common Terminology Criteria for Adverse Events (CTCAE, v5.0) Changes in laboratory (hematology, chemistry) and vital sign parameters Lerapolturev AESIs Anti-PD-1 irAEs Study treatment discontinuation due to AEs Changes from baseline in the number of CD8+ tumor 			
lerapolturev on the TME of injected and non-injected lesions when administered with and without anti-PD-1 therapy	 Changes from baseline in the number of CD8+ tumor infiltrating lymphocytes (TILs) Changes from baseline in PD-L1 expression 			
Secondary To evaluate summivel and	O			
To evaluate survival and disease control outcomes of lerapolturev with and without anti-PD-1, in participants who have failed anti-PD-1/L1-based therapy	 Overall survival (OS): time from treatment group assignment until death from any cause Duration of Response (DOR): time from confirmed objective response (CR or PR per RECIST 1.1) until unequivocal disease progression or death, whichever occurs first Disease control rate (DCR): the proportion of participants achieving confirmed CR, confirmed PR, or stable disease (SD) per RECIST 1.1, as best response Disease control rate-6months (DCR-6mo): the proportion of participants achieving confirmed CR (any duration), confirmed PR (any duration), or SD (≥ 6 months) per RECIST 1.1 as best response Durable Response Rate (DRR): the proportion of participants with confirmed CR or PR (per RECIST 1.1) lasting at least 6 months 			

Confidential Page 48 of 109

	Progression-free survival (PFS): time (number of months) from treatment group assignment until date of documented radiologic disease progression per RECIST 1.1 or death due to any cause, whichever comes first		
Exploratory:			

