5.5 Dose Modification/Toxicity Management Guidelines

5.5.1 Lerapolturev

For AEs related to lerapolturev, lerapolturev may be withheld or permanently discontinued based on the severity of the adverse reaction.

Confidential Page 65 of 109

Holding Lerapolturev Dosing

If a participant experiences any of the following toxicities deemed related to lerapolturev, lerapolturev administration should be held until the toxicity has resolved to at least CTCAE Grade 1 or has returned to baseline:

- Grade 2 or greater irAE, with the exception of vitiligo
- Grade 2 or greater allergic reactions
- any other Grade 3 or greater hematologic or non-hematologic toxicity

For participants receiving concurrent lerapolturev and anti-PD-1 therapy, lerapolturev and the anti-PD-1 therapy can be administered independently of each other where appropriate. Should the investigator determine an AE is related to anti-PD-1 therapy and not lerapolturev, continuation of lerapolturev injections is allowed (or vice versa). However, if the AE is determined to be related to the combination, this should be noted and treatment with both therapies should be held until resolution, as described above.

Permanent Discontinuation:

Lerapolturev should be permanently discontinued if any lerapolturev-related Grade 3 or greater hematologic or non-hematologic toxicity fails to resolve to Grade 1 or baseline OR occurs more than twice (ie, three episodes = permanent discontinuation).

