- Thyroid disorders: Anti-PD-1 products can cause thyroid disorders, including hyperthyroidism, hypothyroidism, and thyroiditis. Participants must be followed for changes in thyroid function (at the start of treatment, periodically every 4 to 6 weeks during treatment, and as indicated based on clinical evaluation) and for clinical signs and symptoms of thyroid disorders per the SOA (Table 1 or Table 2 [Arm 2 lerapolturev + nivolumab]). Hypothyroidism will be treated by replacement hormones. Hyperthyroidism will be managed with thionamides and beta-blockers as appropriate. The anti-PD-1 must be withheld or discontinued for severe (Grade 3) or life-threatening (Grade 4) hyperthyroidism.
- Hyperglycemia: Participants must be regularly monitored for blood glucose or other parameters of Type 1 diabetes. They must be treated with insulin and the anti-PD-1 withheld. In case of severe (Grade 3) hyperglycemia, they will receive anti-hyperglycemics.
- Nephritis: Participants must be evaluated for renal function. They will be given corticosteroids (initial dose of 1 to 2 mg/kg/day prednisone or equivalent followed by a taper) for Grade 2 or greater nephritis. The anti-PD-1 must be withheld for moderate (Grade 2) nephritis and must be permanently discontinuation for severe (Grade 3) or life-threatening (Grade 4) nephritis.
- Skin disorders: Immune-mediated rashes, including Stevens-Johnson Syndrome (SJS) and Toxic Epidermal Necrolysis (TEN) (some cases with fatal outcome), exfoliative dermatitis, and bullous pemphigoid, can occur. Participants must be monitored for suspected severe skin reactions and exclude other causes. Based on the severity of the adverse reaction, the anti-PD-1 must be withheld or permanently discontinued. Participants with Grade 2 or higher dermatologic toxicity will receive topical corticosteroids and/or systemic corticosteroids (initial dose 0.5 1.0 mg/kg/d prednisone or equivalent). For signs or symptoms of SJS or TEN, the anti-PD-1 must be withheld, and the participant must be referred to specialized care for assessment and treatment. In case SJS or TEN is confirmed, the anti-PD-1 must be permanently discontinued.

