To evaluate the antitumor activity of lerapolturev with and without anti-PD-1, in participants who have failed anti-PD-1/L1based therapy	Overall Response Rate (ORR): the proportion of participants achieving confirmed complete (CR) or partial response (PR), per RECIST 1.1 criteria.
To evaluate the safety/tolerability of lerapolturev with and without anti-PD-1, in participants who have failed anti-PD-1/L1based therapy	 The frequency and severity of treatment-emergent adverse events (TEAEs) via National Cancer Institute (NCI) Common Terminology Criteria for Adverse Events (CTCAE, v5.0) Changes in laboratory (hematology, chemistry) parameters Changes in vital sign parameters The frequency and severity of lerapolturev AESI The frequency and severity of anti-PD-1 immune-related AE (irAE) Study treatment discontinuation due to AEs
Secondary	•
To evaluate survival and disease control outcomes of lerapolturev with and without anti-PD1, in participants who have failed anti-PD-1/L1based therapy	 Overall survival (OS): time from treatment group assignment until death from any cause Duration of Response (DOR): time from confirmed objective response (CR or PR per RECIST 1.1) until unequivocal disease progression or death, whichever occurs first Disease control rate (DCR): the proportion of participants achieving confirmed CR, confirmed PR, or SD per RECIST 1.1, as best response Disease control rate-6months (DCR-6mo): the proportion of participants achieving confirmed CR (any duration), confirmed PR (any duration), or SD (≥ 6 months) per RECIST 1.1 as best response Durable Response Rate (DRR): the proportion of participants with confirmed CR or PR (per RECIST 1.1) lasting at least 6 months Progression-free survival (PFS): time (number of months) from treatment group assignment until date of documented radiologic disease progression per RECIST 1.1 or death due to any cause, whichever comes first

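### The SAP's 12-term irAE search list has no thyroid term and only SJS/TEN-type skin terms, so the irAE tables would miss event types the protocol names; the irAE reporting window also needs stating

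*SAP*

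**What the plan says.** Both documents place irAEs among the primary safety endpoints: Protocol Section 2.1 lists "Anti-PD-1 irAEs", and the objectives table in SAP Section 2 specifies their frequency and severity.

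SAP Section 3.2.6 repeats the protocol's definition of an irAE by mechanism. It then gives a list of terms for identifying irAEs: eight high level terms (colitis, lower respiratory, hepatic, hypothalamic/pituitary, adrenal, diabetes, nephritis, encephalitis) and four skin preferred terms (TEN, severe cutaneous adverse reaction, SJS-TEN overlap, SJS). The endocrine and renal part reads "5) HLT: Adrenal cortical hypofunctions; (6) HLT: Diabetes mellitus (incl subtypes); (7) HLT: Nephritis NEC".

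Protocol Section 9.2 refers the reader to Section 5.5 for examples of irAEs. There, under management of anti-PD-1-related irAEs, Section 5.5.2 states: "Anti-PD-1 products can cause thyroid disorders, including hyperthyroidism, hypothyroidism, and thyroiditis". In the skin paragraph, after immune-mediated rashes with SJS and TEN, it adds "exfoliative dermatitis, and bullous pemphigoid, can occur". The dose-hold rule in Section 5.5.1 refers to "Grade 2 or greater irAE, with the exception of vitiligo", which treats vitiligo as an irAE. Section 1.3.1 names rash and pruritis as cutaneous irAEs that the combination might make more frequent or more severe.

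On timing, SAP Section 3.2.6 says "A TEAE is an AE that occurred during the study on or after the initiation of study drug through 30 days after last dose", and also "irAEs are collected through 90 days post last dose of study drug". The irAE row in SAP Section 5.7.1 and the title of Table 14.3.3.2 both carry the treatment-emergent label.

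**The concern.** The list is narrower than the definition it is meant to put into practice. If the irAE tables are programmed from it, hypothyroidism, thyroiditis, immune-mediated rash and vitiligo will not be shown as irAEs, however the investigator judged them. Those tables report a primary safety endpoint. Section 1.3.1 of the protocol also singles out cutaneous irAEs as a possible added risk of the combination, and the list can pick up neither of the two it names there.

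Nothing else in the plan corrects this. SAP Section 5.7.1 has the investigator identify AESIs in the database but states no such route for irAEs. Protocol Section 8.5 lets the SAP prevail where the two differ. SAP Section 7 (changes to planned analyses) and Section 8 (revision history) neither mention nor justify the narrowing.

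The second issue is timing. A treatment-emergent label that ends at 30 days, on events collected for 90, would leave late-onset irAEs out of the irAE summaries.

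**Working it through.** The plan states no irAE rate, so there is no figure to reproduce. The check compares the texts. Matching is by term name, because MedDRA itself was not available.

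**Step 1: protocol irAEs against the SAP list.**

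| Event named in the protocol | Protocol section | Entry on the SAP list |
|---|---|---|
| Pneumonitis | 5.5.2 | lower respiratory HLT |
| Colitis | 5.5.2 | colitis HLT |
| Hepatitis | 5.5.2 | hepatic HLT |
| Hypophysitis | 5.5.2 | hypothalamic/pituitary HLT |
| Adrenal insufficiency | 5.5.2 | adrenal HLT |
| Hyperglycemia / type 1 diabetes | 5.5.2 | diabetes HLT |
| Nephritis | 5.5.2 | nephritis HLT |
| Hyperthyroidism, hypothyroidism, thyroiditis | 5.5.2 | none |
| SJS, TEN | 5.5.2 | own PTs |
| Rash | 1.3.1, 5.5.2 | none |
| Exfoliative dermatitis, bullous pemphigoid | 5.5.2 | none |
| Pruritis | 1.3.1 | none |
| Vitiligo | 5.5.1 | none |

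Infusion-related reactions also appear in the 5.5.2 management section. They are left out because it is unclear that the autoimmune or inflammatory definition covers them.

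**Step 2: counts.**
- Thyroid: 3 named, 0 found.
- Skin: 2 (SJS, TEN) + 1 (rash) + 2 (exfoliative dermatitis, bullous pemphigoid) + 1 (pruritis) + 1 (vitiligo) = 7 named; 2 found; 7 − 2 = 5 missed.

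Protocol Table 4 gives a concrete case. By 10 December 2021, one of 7 crossover participants (14.3%) had lerapolturev-related pruritus. The documents do not call it an irAE, but even if it were one, the list could not show it.

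**Step 3: window.** Collection runs 90 days after last dose; treatment emergence, in SAP Section 3.2.6 and Protocol Section 8.5.3 alike, ends at 30. Read literally, 90 − 30 = 60 days fall outside the irAE summaries, and 60/90 = 67% of the post-treatment collection period.

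**Step 4: sensitivity to one case.** Arm 2 on the QW schedule is planned at about 15 participants. One participant whose only irAE is of an unlisted type changes the reported irAE rate by 1/15 = 6.7 percentage points. How many such participants to expect cannot be worked out, because the documents give no irAE rates by type.

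**The case against.** The strongest counter-argument is that little is actually lost. Thyroid and skin events with onset up to 30 days after last dose still appear in the general TEAE tables (14.3.1.2, 14.3.1.3). Those attributed to anti-PD-1 appear in 14.3.1.4.2 and 14.3.1.5.2, and every AE is in listing 16.2.7.1. TEAE frequency and severity is itself a primary safety endpoint, and the irAE summary is descriptive with no decision rule. All of this stands. It confines the fault to misclassification in the irAE row and Table 14.3.3.2, but those are the outputs that report the irAE endpoint.

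A reader might infer several stronger things that the documents do not support:

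- *That the SAP replaced the protocol's definition.* It keeps the definition; the list fails to match it.
- *That the 30-day cut certainly removes late irAEs.* The SAP never defines a treatment-emergent irAE separately, and it also applies the treatment-emergent label to serious events collected for 90 days. Serious irAEs on days 31-90 may therefore appear in the TESAE tables. The 30-day definition is also the protocol's own. The exposed group is non-serious irAEs, and the fault is an unstated window.
- *That the AESI tables lose events in the same way.* AESIs are identified by the investigator. The protocol expects CRS and ICANS symptoms mainly in the first two weeks of therapy, and injection-site reactions follow injection. No material loss is shown.
- *That a thyroid shift table is missing.* The laboratory endpoint covers hematology and chemistry, and thyroid results are listed (16.2.8.2). Adding one is a preference.

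A fair warning also stands: adding bare rash or pruritus terms would bring in non-immune events, in a trial that injects skin lesions.

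**Conclusion.** The point holds for the term list. By name, the list finds 0 of 3 thyroid disorders and 2 of 7 skin events that the protocol treats as irAEs, so the irAE row and Table 14.3.3.2 would misstate a primary safety endpoint. The ORR analysis is not affected.

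The undercount is certain for the omitted event types, should they occur, but its size in participants is unknown. Any number would rest on an assumed incidence, and the total exposed to the combination depends on crossovers still to come. The net irAE total could even move the other way, because the list has no stated filter for mechanism or relation to anti-PD-1, and entries such as all diabetes subtypes can admit non-immune events.

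On timing, the supported conclusion is that the SAP must state the window. If the literal 30-day reading is applied, non-serious irAEs with onset 31 to 90 days after last dose drop out of the irAE summaries and remain only in the listing.

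The conclusion assumes that the list is applied as written and that matching by term name reflects the MedDRA hierarchy. A MedDRA coder should confirm the second.

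**What to change.** In SAP Section 3.2.6:

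1. Add MedDRA terms for thyroid hypofunction, thyroid hyperfunction and thyroiditis.
2. Add the immune-mediated skin events that the protocol names: exfoliative dermatitis, bullous pemphigoid, vitiligo, rash and pruritus. Count non-specific terms such as rash and pruritus only when the investigator records the event as an irAE. Alternatively, define irAEs as the union of the term list and investigator-recorded irAEs.
3. State that irAE summaries run through 90 days after last dose, and change the irAE row in Section 5.7.1 and the title of Table 14.3.3.2 to match.
4. Record the change in the SAP revision history.

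The cost is SAP wording, a longer term list and some reprogramming. No new data are needed: Protocol Table 8 already sets a 90-day irAE reporting period, and Protocol Section 9.2 already has investigators record irAEs in the eCRF. Confirm that the eCRF entry distinguishes irAEs from other AEs, since the filter in step 2 depends on it.
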